- *** Be certain to record concomitant medications at the time of dosing/randomization, including vaccine administered in the 14 days prior to Visit 01, during Visit 01, and up to 14 days after Visit 01. Concomitant reportable medications will be collected in the event of an AE (including an LRTI hospitalization) through a phone contact by the medical call center or through the participant's medical records, as applicable. Sites will also be asked to report any routine immunization with nirsevimab (Beyfortus®). See Section 6.8 for details on concomitant reportable medications.
- ††† Vaccine history is to be recorded in the eCRF. This includes vaccines co-administered during Visit 01, as well as vaccines administered up to 14 days before and up to 14 days after dosing/randomization.
- ‡‡‡ Immunization is only for Group 1, the nirsevimab arm. Participants randomly assigned to Group 2 will receive no RSV preventive intervention.
- Parents or LARs of the participant will be instructed to keep a study card that indicates study participation. The study card is to be presented to the hospital in the event of hospitalization due to any cause. The site or the Investigator's contact details should be reported on it.
- **** A safety follow-up phone contact is to be made at 18 months and at 24 months post-dosing/randomization for UK reconsented participants only. During these calls, the investigator or site staff will interview the participant's parents/LARs to review the memory aid and collect any information on SAE or LRTI hospitalizations that may have occurred since the previous contact. If an SAE is reported, the investigator or site staff will assess the relationship and only related SAE will be reported in the eCRF.
- †††† Consent of the Addendum to Informed Consent Form can be obtained from parents/LARS at any time prior or after the D366 phone call (up to D731). An electronic ICF process or consent by email can be implemented if applicable as per country regulations. Following the D366 phone call, an on-site visit can be organized for participants' parents/LARs unable to realize the e-consent or email consent in order to collect the paper consent.
- ‡‡‡‡ Only concomitant medication related to related SAE and/or LRTI hospitalization will be collected. Sites will also be asked to report any routine immunization with nirsevimab (Beyfortus).

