5.1. Time Points and Visit Windows

5.1.1. General Definitions

All assessment days will be related to Day 1. Day 1 is the date of randomization (for no intervention group) / immunization (for nirsevimab group).

Relative days after Day 1 are calculated as (assessment date – Day 1 date) + 1. Relative days prior to Day 1 are calculated as (assessment date – Day 1 date). The day prior to Day 1 is Day -1. Day 0 is not defined.

The date of the immunization for each participant in the nirsevimab group will be taken from the Immunization eCRF page. If the date on this eCRF page is missing, alternatively the date of randomization will be used.

The date of the randomization for each participant in the no intervention group will be taken from the Randomization eCRF page. If the date in this eCRF page is missing, alternatively the date of informed consent (Informed Consent Date eCFR page) will be used.

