6.7.2. Adverse Events

6.7.2.1. Definitions/ Derivations

All AEs recorded on the eCRF will be coded using the MedDRA dictionary (version 25.0) and classified as treatment-emergent AEs (TEAEs) as follows:

- Pre-treatment AEs are events
 - that start prior to the start of the Treatment Period and with a stop date before the Treatment Period
- or
- with a stop date after the start of the Treatment Period or with a missing stop date, but with a grade lower or equal to 1.
- TEAEs are either events
 - with the start date and time posterior to the start of the Treatment Period and up to the end of the Treatment Period

or

- events with the start date and time prior to the start of the Treatment Period
 - whose severity is greater than 1 or missing
- and
 - stop date is missing or not before the Treatment Period.
- Treatment-Emergent Serious AEs will be defined as TEAEs where Serious = “Yes”
- The relationship between a TEAE and treatment is assessed as related, or not related. A treatment-related TEAE will be defined as a TEAE considered by the investigator as related or, with unknown / missing relationship to treatment for participants who received nirsevimab on Day 1. An unknown / missing relationship between a TEAE and treatment for participants who received no intervention will be considered as not related.
- Assessment of AE intensity will be based on the AEs intensity grading scales adapted from the “FDA Guidance for Industry: Toxicity Grading Scale for Healthy Adult and Adolescent Volunteers Enrolled in Preventive Vaccine Clinical Trials, September 2007”
- TEAEs leading to discontinuation of study are defined as TEAEs where “Caused Study Discontinuation” is indicated as “Yes”.
- Pyrexia includes those adverse events with PT term equal to ‘Pyrexia’.
- Injection site reactions include those adverse events with category of adverse event equal to ‘IMP Injection/Administration Site Reaction’ or ‘Other Vaccination Injection/Administration Site Reaction’.
- Rash includes those adverse events with PT term equal to ‘Erythema’, ‘Rash’, ‘Rash macular’, ‘Rash maculo-papular’ or ‘Urticaria’.

In addition to the aforementioned AE types, TEAEs of special interest will be identified in eCRF (Is the event an AESI = Yes):

- Hypersensitivity, including anaphylaxis
- Immune complex disease
- Thrombocytopenia

Immediate AEs are recorded to capture medically relevant AEs which occur within the first 30 minutes after immunization.

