6.7.2.2. Analyses

Adverse events will be summarized by default descriptive summary statistics for categorical variables for the SafAS by treatment group and overall as follows:

- An overview of TEAEs (#) including the number and percentage of participants with at least one of each mentioned TEAE type provided with 95% Clopper-Pearson confidence interval:
 - Any TEAE
 - Leading to discontinuation of study
 - Leading to death
 - Grade 1 severity
 - Grade 2 severity
 - Grade 3 severity
 - Any study treatment related TEAE
 - Leading to discontinuation of study
 - Leading to death
 - Grade 1 severity
 - Grade 2 severity
 - Grade 3 severity
 - Any serious TEAE
 - Leading to discontinuation of study
 - Leading to death
 - Any serious study treatment related TEAE
 - Leading to discontinuation of study
 - Leading to death
 - Non-serious TEAEs until 30 days after Day 1
 - Leading to discontinuation of study
 - Grade 1 severity
 - Grade 2 severity
 - Grade 3 severity
 - Any immediate TEAEs reported in the 30 minutes after immunization
 - Leading to discontinuation of study
 - Leading to death

- Grade 1 severity
 - Grade 2 severity
 - Grade 3 severity
 - Medically-attended TEAEs
 - Leading to discontinuation of study
 - Leading to death
 - Grade 1 severity
 - Grade 2 severity
 - Grade 3 severity
 - TEAEs of Special Interest
 - Leading to discontinuation of study
 - Leading to death
 - Grade 1 severity
 - Grade 2 severity
 - Grade 3 severity
- The number and percentage of participants reporting each TEAE and the number of events as well as 95% Clopper-Pearson confidence interval will be summarized by SOC and PT for the following types of TEAEs:
 - Non-serious TEAEs through Day 31 post-dosing/randomization (*)
 - Immediate TEAEs reported in the 30 minutes post-dosing/ randomization (*)
 - Medically-attended TEAEs (*) (#)
 - TEAEs of Special Interest (*) (#)
 - TEAEs Leading to Death
 - TEAEs by Maximum Intensity (*) (#)
 - TEAEs by Relationship to Treatment (*) (#)
 - Study Treatment related TEAEs Leading to Death (*)
 - Serious TEAEs (*) (#)
 - Study Treatment Related Serious TEAEs (#)
 - Study Treatment Related TEAEs (*) (#)
- The number and percentage of participants who died will be summarized by the primary cause of death

All AE tables mentioned above will also be repeated for the following subgroups:

- ✓ By country
- ✓ By weight group (< 2.5 kg, < 5 kg, ≥ 5 kg)
- ✓ By age group (neonate participants, randomization stratification)

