In addition, all AE tables by SOC and PT listed above and flagged with (*) will also be repeated in participants who received other vaccines:

- ✓ On the same day as nirsevimab
- ✓ Within 7 days before or after nirsevimab immunization
- ✓ Within 14 days before or after nirsevimab immunization.

For the subgroups about participants who received other vaccines, see [Table 6](#) from Appendix 2 (Section 8.2) to get the vaccines to be considered.

Moreover, below tables will be produced:

- ✓ Non-serious TEAEs through Day 31 post-dosing/randomization by SOC and PT in at least 1% of participants
- ✓ Medically-attended TEAEs by SOC and PT in at least 1% of participants
- ✓ TEAEs through Day 7 post-dosing/randomization by SOC and PT
- ✓ TEAEs through Day 7 post-dosing/randomization by SOC and PT - Pyrexia
- ✓ TEAEs through Day 7 post-dosing/randomization by SOC and PT - Injection Site Reactions
- ✓ TEAEs through Day 14 post-dosing/randomization by SOC and PT
- ✓ TEAEs through Day 14 post-dosing/randomization by SOC and PT - Rash

Study Treatment Related Serious TEAEs tables by SOC and PT (overall and by subgroups) and with the number of events as well as 95% Clopper-Pearson confidence interval will also be produced at the time of Second Year Analysis in UK re-consented participants for the below periods:

- ✓ From 366 Days Post-Dosing/Randomization to 731 Days Post-Dosing/Randomization.
- ✓ From Day 1 to 731 Days Post-Dosing/Randomization
- ✓ From Day 1 to 366 Days Post-Dosing/Randomization

The summary table of TEAE will also be produced at the time of Second Year Analysis in UK re-consented participants for the below periods;

- ✓ From 366 Days Post-Dosing/Randomization to 731 Days Post-Dosing/Randomization.
- ✓ From Day 1 to 731 Days Post-Dosing/Randomization
- ✓ From Day 1 to 366 Days Post-Dosing/Randomization

For the period “From 366 Days Post-Dosing/Randomization to 731 Days Post-Dosing/Randomization”, only below TEAE will be presented:

- TEAE with a start date on or after Day 366,
- TEAE with a start date before Day 366 but ongoing at Day 366 (no stop date or with a stop date after Day 366).

For summaries by maximum intensity, participants with multiple TEAEs within a particular SOC or PT will be counted under the category of their most severe TEAE within that SOC or

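### The three co-vaccination safety subgroups in SAP 6.7.2.2 are timed from the nirsevimab injection, so read literally they hold no undosed controls and give no vaccine-only comparator

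*SAP*

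**What the plan says.** SAP 6.7.2.2 opens its adverse event output with a general layout: "Adverse events will be summarized by default descriptive summary statistics for categorical variables for the SafAS by treatment group and overall as follows". It later adds that "all AE tables by SOC and PT listed above and flagged with (*) will also be repeated in participants who received other vaccines". Three subgroups follow: "On the same day as nirsevimab", "Within 7 days before or after nirsevimab immunization" and "Within 14 days before or after nirsevimab immunization". The vaccines that count are those listed in SAP Appendix 2.

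The data and the date conventions cover both arms. The footnotes to the Schedule of Activities (Protocol 1.3) require recording of vaccines given at Visit 01 and of "vaccines administered up to 14 days before and up to 14 days after dosing/randomization"; Protocol 6.8 says the same. SAP 5.1.1 sets a common origin: "Day 1 is the date of randomization (for no intervention group) / immunization (for nirsevimab group"). The vaccine-use tables in SAP 6.4.3 use a 14-day window around dosing or randomization.

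For the Day 7 injection-site table, SAP 6.7.2.1 selects events with "category of adverse event equal to ‘IMP Injection/Administration Site Reaction’ or ‘Other Vaccination Injection/Administration Site Reaction", so both categories enter one table.

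**The concern.** Co-administration is the expected use. Protocol 2.3.2 anticipates giving nirsevimab at the same visit as routine vaccines, Protocol 4.2 relies on this for delivery, and Protocol 6.8 says vaccines due at the enrollment visit should go ahead. Someone using the co-vaccination tables will want to know whether nirsevimab plus a vaccine is followed by more events than the vaccine alone.

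A table of co-vaccinated nirsevimab recipients cannot answer that without a column of vaccinated controls. The trial collects what is needed for that column, and the chosen anchor leaves it out. At stake is the usefulness of a set of safety tables, within the secondary objective of characterizing safety. No hypothesis test depends on it.

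**Working it through.** **1. Who can enter the subgroups.** The documents state no figure for these subgroups, so there is none to reproduce; this is a reading of the text.

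| Step | Source | Content |
|---|---|---|
| Population | SAP 4.4 | Control members of the Safety Analysis Set are those who did not receive nirsevimab; analysis is by intervention received |
| Entry condition | SAP 6.7.2.2 | Another vaccine on the day of nirsevimab, or within 7 or 14 days of it |
| Columns | SAP 6.7.2.2 | By treatment group and overall |

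All three entry conditions need a nirsevimab date, and undosed controls have none. A control dosed inadvertently is counted under nirsevimab. Eligible undosed controls: **0**.

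**2. Whether another table fills the gap.**
- No other planned adverse event table is restricted to vaccinated controls, or to nirsevimab recipients without a co-administered vaccine.
- The Day 7 tables (all events, pyrexia, injection-site reactions) and Day 14 tables (all events, rash) fall under the by-arm layout, so they compare whole arms, averaged over vaccination status. They are not among the flagged tables repeated in the co-vaccinated subgroups.
- The flagged set includes tables by relationship to treatment. These rest on open-label investigator judgment. Under SAP 6.7.2.1, a missing relationship counts as related for nirsevimab recipients and as not related for the no intervention group.

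**3. What the missing column could hold.** The planned arm size is 14,430 (Protocol 9.2). Uptake *f* and event rate *p* are assumptions, since the documents give neither.

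Infants per arm: n = 14,430 × f. A 95% half-width for the difference between two arms with equal rates: 1.96 × √(2p(1 − p)/n).

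For f = 10%, p = 5%: n = 1,443, and 1.96 × √(2 × 0.05 × 0.95 / 1,443) = 0.0159, or 1.59 percentage points.

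| Assumed uptake | n per arm | Half-width, p = 1% | p = 5% | p = 10% |
|---|---|---|---|---|
| 10% | 1,443 | 0.73 | 1.59 | 2.19 |
| 25% | 3,608 | 0.46 | 1.01 | 1.38 |
| 50% | 7,215 | 0.32 | 0.71 | 0.98 |

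Half-widths are in percentage points. They show only that the omitted column would carry information; the SAP plans no tests on adverse events.

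**4. The injection-site table.** An undosed control cannot have a reaction at the study-product site, so that column can contain only reactions to other vaccines. The nirsevimab column can contain both kinds. Rows are by system organ class and preferred term, and the category only decides which events enter. The category is recorded, so the two sources can be shown apart from data in hand.

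**The case against.** **It may be loose wording.** The repeated tables are by treatment group, and the documents sometimes use immunization for both arms: Protocol 8.3.2 collects serious events in all participants until 12 months after it. SAP 6.7.2.2 itself refers immediate events to immunization in one list and to dosing or randomization in another. This is plausible, and the text does not settle intent. It supports clarifying the wording, because a programmer following the SAP as written would produce an empty control column.

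**Describing co-vaccinated recipients is legitimate in itself.** No objective or endpoint names co-administration, and the SAP states that adverse events will not be compared statistically between groups. Both points stand and limit the weight of the concern. A descriptive table can still show two columns, as its parent tables do.

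**Stronger readings that the documents do not support.**
- A reader might infer that reactions to nirsevimab and to routine vaccines cannot be told apart anywhere. The relationship tables, the separate recorded injection-site categories and the whole-arm Day 7 and Day 14 tables each give partial separation.
- A reader might infer that both kinds of local reaction fall in one row. Rows are preferred terms and the layout sits in the table shells, which are not part of these documents, so this is not shown.
- A reader might take vaccinated controls for a clean randomized comparator. Day 1 is the day of randomization and allocation is open-label, so a vaccine at Visit 01 could be given or deferred once allocation is known. The instruction in Protocol 6.8 to give scheduled vaccines as planned lessens this risk but does not remove it.

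**Conclusion.** The point holds in a limited form and is worth correcting. Read literally, the three subgroups contain no undosed controls, so these tables cannot by themselves show whether nirsevimab adds to events that follow routine vaccines. No other planned adverse event table supplies that comparator.

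The size in the documents' own terms is zero controls. Under assumed uptake of 10% to 50%, about 1,443 to 7,215 controls would enter. For an event with an assumed 5% rate, the difference between arms would have a 95% half-width of about 1.6 down to 0.7 percentage points. These figures depend on the planned enrollment being reached and on similar uptake in the two arms.

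The consequence is confined to descriptive safety output. The primary and key secondary conclusions do not depend on it.

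**What to change.** In SAP 6.7.2.2, time all three windows from Day 1 as defined in SAP 5.1.1 (immunization for nirsevimab, randomization for no intervention), in line with the vaccine-use tables in SAP 6.4.3. Show both arms, descriptively, with the Clopper-Pearson intervals already planned.

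Make same-day vaccination the main subgroup, because the 7- and 14-day windows also select on vaccines given after Day 1. Report same-day vaccine uptake by arm beside it, and state that vaccination on or after Day 1 may depend on allocation.

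The added column will not help in every repeated table. The 30-minute observation applies only to the nirsevimab group (Protocol 8.3.2), so the immediate-event table should say that controls were not observed.

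In the Day 7 injection-site table, present the study-product-site and other-vaccination-site categories separately.

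Cost: a wording change and somewhat more table output, with no new data. The resulting comparison is descriptive and not fully protected by randomization, and the table notes should say so.

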6.7.3. Laboratory Evaluations

Not Applicable

6.7.4. Vital Signs

Not Applicable.

6.7.5. Electrocardiograms

Not Applicable.

6.7.6. Physical Examination

Not Applicable.

6.7.7. Other Safety Variables

Not Applicable.

6.7.8. Planned Analyses and Data Monitoring

There will be 3 planned main analyses for this study: the Primary Analysis, the First Year Analysis and the Second Year Analysis.

The Primary Analysis will be conducted when at least 61 events of RSV LRTI hospitalization in all 3 countries combined are observed, but no later than 30 April 2023. All available data collected up to the data cut-off date will be analyzed at the time of the Primary Analysis.

The First Year Analysis will be conducted when all participants have completed the scheduled 12-month safety follow up. It will include all data and planned analyses. The Second Year Analysis will be conducted when all UK reconsented participants have completed the scheduled 24-month safety follow-up. It will include all data and planned analyses. In order to present results from the First Year Analysis or Second Year Analysis, results may be generated before the formal lock of data for abstract purposes. Updates of the data will be done with the formal database locks.

A Primary Analysis is planned prior to the formal completion of the study. The efficacy analyses planned in the Primary Analysis will serve the purpose of evaluating the efficacy of nirsevimab in the study population.

In addition, Primary Analysis outputs will also be rerun at the time of First Year Analysis still with the same cut-off date in order to consider potential new data collected after the cut off date due to the delay in the data collection (see Section 6.6.7.10 for details).

RSV LRTI hospitalization will also be collected after the end of the RSV season and the efficacy will be calculated but only for descriptive purposes at the time of the First Year Analysis without the intention of a confirmatory conclusion.

This will also be collected at 24 months follow-up in UK reconsented participants but only for descriptive purposes at the time of the Second Year Analysis without the intention of a confirmatory conclusion.

In addition, recurrent wheeze event will be collected at the 12 and 24 months follow-up, in UK reconsented participants only for descriptive purposes at the time of the Second Year Analysis.

Therefore, no multiplicity adjustment is needed for the 3 main analyses (Primary, First Year and Second Year) of the primary endpoint.

As per protocol, participants safety will be continuously monitored by the Sponsor's internal safety review committee which includes safety signal detection at any time during the study. The sponsor's internal safety review committee will be responsible for the unblinded review, assessment, and evaluation of safety data generated from this study. As described in the Safety Management Team Charter, these unblinded reviews will monitor AESIs, SAEs, AEs and MAAEs (including LRTI).

6.8. Pharmacokinetic Assessments

Pharmacokinetics parameters are not evaluated in this study.

6.9. Transparency

At the Second Year Analysis, for transparency (ClinicalTrials.gov (CTGov) and European Union Drug Regulating Authorities Clinical Trials (EudraCT)), some outputs will also be programmed using XML language (for AE) and produced in RTF and PDF (for others). They will be generated but not presented in any appendix, nor in the Clinical Study Report.

For Clinical Trial Registry, it will correspond to:

- ✓ Participant Disposition – Reason for discontinuation
- ✓ Disposition of Randomized participants by Country
- ✓ Demographic Characteristics
- ✓ Demographic Characteristics by EudraCT Categorical Age:
 - Newborns defined as age ≤ 27 days
 - Infants and Toddlers defined as age between 28 days (included) and 23 months (included)
- ✓ Overview of Number of Participants with TEAE
- ✓ Overview of Adverse Events

- ✓ Number of Participants/Events with Treatment Emergent SAEs by SOC and PT for CTGov
- ✓ Number of Participants/Events with Treatment Emergent SAEs by SOC and PT for EudraCT
- ✓ Number of Participants/Events with Treatment Emergent Non Serious Adverse Events (SAEs) with PT > 5 % in any Treatment Group by SOC and PT for CTGov
- ✓ Number of Participants/Events with Treatment Emergent Non Serious Adverse Events (SAEs) with PT > 5 % in any Treatment Group by SOC and PT for EudraCT

In addition, the following lay outputs for TEAE related to treatment will also be produced:

- ✓ Overview of Side Effect Profile: Treatment Emergent Side Effects
- ✓ Number (%) of Participants with Treatment Emergent Serious Side Effects by Lay PT
- ✓ Number (%) of Participants with Treatment Emergent Side Effects Leading to Death by Lay PT
- ✓ Number (%) of Participants with Treatment Emergent Side Effects Leading to Study Discontinuation by Lay PT
- ✓ Number (%) of Participants with Treatment Emergent Non Serious Side Effects by Lay PT
- ✓ Number (%) of Participants with Treatment Emergent Serious Side Effects by Lay SOC and Lay PT

7. Changes in the Conduct of the Study or Planned Analysis

The following changes in the protocol-planned analyses were performed:

- ✓ SDI deciles were updated using a SAS function for Primary Analysis
- ✓ For LRTI description, the rule “*If participants have multiple hospitalizations (respectively ICU stay) during the follow up period, duration of hospitalization (respectively ICU stay) will be the sum of each duration of hospitalization (respectively ICU stay)*” was finally not applied for Primary Analysis and will not be considered for First Year Analysis.

The following changes were performed for First Year Analysis:

- ✓ Incidence of hospitalizations for all-cause LRTI through Day 181 post-dosing/randomization will also be analysed by country
- ✓ Incidence of very severe RSV LRTI defined as RSV LRTI hospitalization with oxygen saturation < 90% (at any time during hospitalization) and oxygen supplementation, through Day 181 post-dosing/randomization will also be described by country

Tables for transparency will also be produced at the time of Second Year Analysis.

The Primary Analysis was re-run at the time of the First Year Analysis considering the same cut-off date and the same rules as the Primary Analysis.

An additional intercurrent event was added to consider participants who received Beyfortus as a routine medication during the study. They are excluded from the Per-Protocol Analysis Set and some analyses and listings are produced restricted to these specific participants (if at least 10 participants for tables / if at least one participant for listings).

8. Appendices

